6.5.1 Efficacy Assessments

The effect of CR845 on itch will be measured by the following PRO measures:

- Worst Itching Intensity NRS score
- Skindex-10 Scale
- 5-D Itch Scale
- Patient Global Impression of Change (PGIC)
- Patient Global Impression of Worst Itch Severity

Patients will be trained on completion of the Worst Itching Intensity NRS scale at the first day of the Run-in Period, and will be trained on Skindex-10 Scale, 5-D Itch Scale, Patient Global Impression of Worst Itch Severity, and PGIC worksheets at any time during the Run-In Period or on Day 1 of the Treatment Period. All questionnaires must be completed in strict adherence to the Patient Reported Outcomes Instructions (as per Study Reference Manual).

6.5.1.1 Worst Itching Intensity Numerical Rating Scale

Intensity of itch will be measured using an NRS scale ([Appendix 2, Section 14.2](#)) on a worksheet on which patients will be asked to indicate the intensity of the worst itching they experienced over the past 24 hours by marking one of 11 numbers, from 0 to 10, that best describes it, where “0” is labeled with the anchor phrase “no itching” and “10” is labeled “worst itching imaginable.” Patients will be provided with these worksheets to record their 24-hour worst itching assessment scores.

The Worst Itching Intensity NRS has been widely utilized for evaluation of chronic itch, including uremic pruritus [[Kumagai 2010](#); [Pisoni 2006](#); [Mathur 2010](#); [Ständer 2013](#)].

6.5.1.2 Skindex-10 Scale

Developed specifically for uremic pruritus, the Skindex-10 Scale ([Appendix 3, Section 14.3](#)) is an instrument for measurement of quality of life that correlates with both itch intensity as well as other instruments evaluating quality of life in patients with uremic pruritus [[Mathur 2010](#)]. Patients are asked to fill in 1 of 7 circles numbered from 0 (labeled with the anchor phrase “never bothered”) to 6 (labeled as “always bothered”) for each of the 10 questions. The total score is the sum of the numeric value of each answered question. The total score is subdivided into 3 domain scores, which are sums of the scores of the following questions: disease domain (questions 1 to 3), mood/emotional distress domain (questions 4 to 6), and social functioning domain (questions 7 to 10).

6.5.1.3 5-D Itch Scale

The 5-D Itch Scale was developed as a brief, but multidimensional questionnaire designed to be useful as an outcome measure in clinical trials. The 5 dimensions of itch assessed are degree, duration, direction, disability, and distribution ([Appendix 4, Section 14.4](#)). The scale has been validated in patients with chronic pruritus and has been shown to be sensitive to changes in pruritus over time [[Elman 2010](#)].

6.5.1.4 Patient Global Impression of Change

The PGIC is a global PRO measure that assesses the change (improvement or worsening) in overall status relative to the start of the study [[Dworkin 2005](#)]. The scale has only 1 item, with values ranging from 1 (Very Much Improved) to 7 (Very Much Worse) ([Appendix 5, Section 14.5](#)).

6.5.1.5 Patient Global Impression of Worst Itch Severity

The Patient Global Impression of Worst Itch Severity is a PRO measure that assesses itch severity [[Guy 2000](#)]. The scale has only 1 item, with 5 possible values ranging from none to very severe ([Appendix 6, Section 14.6](#)).

6.5.2 Safety Assessments

The safety assessments for each patient are the following:

- Severity, seriousness, and relationship of adverse events to study drug
- Physical examination
- Vital signs
- 12-lead ECGs
- Clinical laboratory tests

6.5.2.1 Adverse Events

6.5.2.1.1 Definition of Adverse Event

An adverse event is any untoward medical occurrence in a patient or clinical investigation subject administered a medicinal product and that does not necessarily have to have a causal relationship with this treatment. An adverse event can therefore be any unfavorable and unintended sign (including an abnormal laboratory finding, for example), symptom, or disease temporally associated with the use of a medicinal product, whether or not considered related to the medicinal product.

In this study, adverse events will be captured from the time a patient signs the ICF to the Follow-up Visit and include the following:

- Any new sign, symptom, or disease;
- Any new clinically significant or symptomatic laboratory/diagnostic test abnormality;
- Any clinically significant worsening of laboratory/diagnostic test abnormality;
- Any worsening (ie, clinically significant change in frequency, nature and/or intensity) of a pre-existing condition.

A pre-existing condition is a condition that is present prior to signing the ICF for the study. Pre-existing conditions, such as illnesses, symptoms, reactions, progression of disease states, and other comorbidities, as well as pre-existing laboratory/diagnostic test abnormalities, will be documented in the patient's record as medical history.

Signs and symptoms will be reported individually as adverse events (non-serious), unless a medical diagnosis was provided. Medical diagnosis, whenever provided, will be reported rather than individual signs and symptoms.

Any adverse event that satisfies any of the seriousness criteria described in [Section 6.5.2.1.3](#) will be reported as a serious adverse event (SAE) using the SAE Report Form, in addition to documenting in the eCRF.

6.5.2.1.2 Adverse Event Severity Assessment

The Investigator will assess the severity (ie, intensity) of each adverse event (serious and non-serious) reported during the study based on his/her clinical judgment. The severity of each adverse event will be assigned to one of the following categories:

Mild: Transient, requires no special treatment, is easily tolerated by the patient, causes minimal discomfort, and does not interfere with the patient's daily activities

Moderate: Introduces a level of inconvenience or concern to the patient that may interfere with daily activities, but usually is ameliorated by simple therapeutic measures

Severe: Interrupts a patient's usual daily activity and requires systemic drug therapy or other treatment

6.5.2.1.3 Definition of Serious Adverse Events

An SAE is any untoward medical occurrence that:

- Results in death;
- Is life-threatening;

NOTE: The term "life-threatening" in the definition of "serious" refers to an event in which the patient was at risk of death at the time of the event; it does not refer to an event that hypothetically might have caused death if it were more severe.

- Requires inpatient hospitalization or prolongation of existing hospitalization;
- Results in persistent or significant disability/incapacity; or
- Is a congenital anomaly/birth defect.

Medical and scientific judgment should be exercised in deciding whether expedited reporting is appropriate in other situations, such as important medical events that may not be immediately life-threatening or result in death or hospitalization, but may jeopardize the patient or may require intervention to prevent one of the other outcomes listed in the definition above. These are usually considered serious.

6.5.2.1.4 Severe vs Serious Adverse Event

The term "severe" is used to describe the intensity (severity) of a specific event (as in mild, moderate, or severe myocardial infarction); the event itself, however, may be of relatively minor medical significance (such as severe headache). An adverse event as well as an SAE must be assessed for severity. An adverse event that is assessed as severe should not be confused with an SAE. "Severity" is not the same as "serious," which is based on patient outcome or reaction criteria usually associated with events that pose a threat to a patient's life or functioning. Seriousness (not severity) serves as a guide for defining regulatory reporting obligations.

6.5.2.1.5 Adverse Event Causality or Relatedness to the Study Drug

Every effort should be made by the Investigator to explain each adverse event and assess its relationship, if any, to study drug. The Investigator should consider many factors, including, but not limited to, temporal association of the event and date/time of study

drug, duration of study drug, medical/biologic plausibility, pharmacology and adverse event profile of study drug, medical history (past medical history, underlying disease, comorbidities, intercurrent illness), concomitant medications, medical judgment, dechallenge, rechallenge, drug interaction, other plausible causes, etc., to determine the causality assessment of an event.

The Investigator as well as the Sponsor will determine adverse event/SAE causality as ‘Related’ or ‘Not Related’ to study drug. Although there is no international consensus on how to define ‘Related’ and ‘Not Related,’ in general, an event is considered ‘Related’ if there is reasonable possibility that the event is related to study drug than to any other possible cause(s). Conversely, an event is considered ‘Not Related’ if there is reasonable possibility that the event is related to other factors than the study drug.

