Patients will report their Worst Itching Intensity NRS score over the last 24 hours daily during the entire Treatment Period. Patients will be instructed to complete the NRS score at a similar time of the day throughout the Treatment Period. In addition, patients will complete other patient-reported outcome (PRO) measures (Skindex-10 Scale, 5-D Itch Scale, Patient Global Impression of Worst Itch Severity) during the Treatment Period. The PGIC will be completed at end of treatment/early termination.

Safety assessment will be monitored periodically as per schedule of events ([Table 2](#)). Adverse events and concomitant medications will be recorded during the study starting at Screening until the Follow-up Visit. A final safety Follow-up Visit will be conducted 7 to 10 days after the last dose of study drug.

The study schematic is shown in [Figure 1](#).

Figure 1. CR845-210301 Study Schematic

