6.5.2.1.6 Adverse Event Documentation and Follow-up

All adverse events, including observed, elicited, or volunteered problems, complaints, or symptoms are to be recorded on the adverse event page in the patient’s eCRF from the time the patient signs the ICF until the Follow-up Visit/early termination, whether or not judged by the Investigator to be related to study drug. The need to capture this information is not dependent upon whether adverse events are related to study drug. Serious adverse events that occurred up to 30 days after the last dose of study drug need to be documented on an SAE Report Form if they are deemed by the Investigator to be “Related” to study drug.

Each adverse event is to be documented with a verbatim/reported term, start and stop date, severity, causal relationship to study drug, action taken with study drug, and outcome (resolved, resolved with sequelae, resolving, not resolved, fatal, unknown). The Investigator must review new adverse events and the outcome of ongoing adverse events frequently throughout the study.

In addition to recording all adverse events (serious and non-serious) in the patient’s eCRF, all SAEs must also be documented on the SAE Report Form for the study.

The Investigator will follow all adverse events until they resolve, the Investigator assesses them to be stable, or the patient’s participation in the study ends, whichever comes first. In addition, the Investigator will follow all adverse events assessed as related to study drug that are ongoing at the time of the patient’s last visit, until they resolve or the Investigator assesses them as stable, even if the patient’s participation in the study has ended. Resolution of such events is to be documented in the patient’s record as appropriate.

It is anticipated that some patients may undergo procedures and/or experience events that are common in the study population under investigation, independent of study therapy. Preplanned procedures and procedures (eg, kidney transplant or catheter replacement) or events that are independent of study therapy, according to the Investigator’s assessment, will be documented as specified in the Safety Management Plan.

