6.5.2.1.7 Serious Adverse Event Notification, Documentation, and Reporting

The Investigator will report an SAE within 24 hours of becoming aware of the event. An SAE Report Form will be completed regardless of relationship to the study drug. The initial report will not be delayed in order to obtain additional information. Any additional information will be reported as a follow-up to the initial report within 24 hours of collection.

Details for reporting and follow-up of SAEs are provided in the Safety Management Plan.

In the event of any SAE (other than death) occurring after the last dose of study drug and prior to the Follow-up Visit, the patient will be instructed to contact the Investigator or designee immediately using the instructions provided on the ICF.

The Medical Monitor will review reported SAEs and may contact the Investigator directly for further information.

The Sponsor will comply with the applicable local regulatory requirements related to reporting of SAEs to the Food and Drug Administration (FDA), while the Investigator and designated study personnel will comply with the applicable local regulatory requirements related to reporting of SAEs to the IRB and Sponsor.

It is the responsibility of Cara Therapeutics to send all regulatory reports to the FDA. Adverse events that are serious, related to the study drug, and unexpected (per the [Investigator's Brochure](#)) will be reported to the FDA as per Code of Federal Regulations 21 Code of Federal Regulations (CFR) 312.32 on Investigational New Drug safety reporting and as specified in the Safety Management Plan.

For regulatory reporting purpose, the sponsor will follow “Guidance for Industry and Investigators - Safety Reporting Requirements for INDs and BA/BE Studies” (December 2012), which states “for serious events that are unexpected, the sponsor considers the investigator’s causality assessment but submits an IND safety report only for those events for which the sponsor determines there is a reasonable possibility that the drug caused the event, regardless of the investigator’s causality assessment.”

As applicable, the Sponsor will also notify other participating Investigator(s) of all Investigational New Drug Safety Reports to ensure prompt notification of significant new adverse events or risks with respect to study drug. This notification will occur as soon as possible and in compliance with country-specific regulations.

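### Related and Not Related are not complementary definitions, so an adverse event with two plausible causes can be labelled Not Related

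*Protocol*

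**What the plan says.** Protocol 6.5.2.1.5 lists factors for the Investigator to weigh (timing, pharmacology, comorbidities, concomitant medication, dechallenge and others). It then says: "The Investigator as well as the Sponsor will determine adverse event/SAE causality as" Related or Not Related. In general, an event is Related "if there is reasonable possibility that the event is related to study drug than to any other possible cause(s", and conversely it is Not Related "if there is reasonable possibility that the event is related to other factors than the study drug". Nothing says what to do when an event meets both.

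The label is then used in these places:

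- **Late SAEs (Protocol 6.5.2.1.6).** "Serious adverse events that occurred up to 30 days after the last dose of study drug need to be documented" on an SAE form on condition that the Investigator deems them Related. General capture is shorter: under 6.5.2.1.1, "adverse events will be captured from the time a patient signs the ICF to the Follow-up Visit". Section 6.1 sets that visit: "A final safety Follow-up Visit will be conducted 7 to 10 days after the last dose of study drug".
- **Follow-up after participation (Protocol 6.5.2.1.6).** The duty to continue beyond the last visit, to resolution or stability, is limited to Related events: "will follow all adverse events assessed as related to study drug that are ongoing at the time". Other events are followed only until participation ends.
- **Tables.** Related-TEAE summaries are planned in Protocol 8.7.2 and SAP 8.7.1, and a table of related AEs in the interim package of SAP 8.9.2.5.

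Protocol 6.5.2.1.7 uses another test for IND safety reports on unexpected serious events: a report is sent only where "the sponsor determines there is a reasonable possibility that the drug caused the event". That test makes no comparison with other causes.

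**The concern.** A binary causality field needs two definitions that cover every case once. Here each label has its own positive criterion, and the criterion for Not Related does not ask whether a drug cause is unlikely.

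This matters more in a population where competing explanations are expected. Protocol 6.5.2.1.6 itself anticipates events that are common in these patients whatever the study therapy. The most common adverse events named in Protocol 4.3 include non-specific ones such as dizziness, fatigue and somnolence. Two investigators could label the same event differently, each within the text.

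At stake are the completeness of SAE documentation after the Follow-up Visit, outcome information on events still ongoing when a patient leaves the study, and the meaning of the related-event tables, including the one produced at an interim analysis that may drop poorly tolerated doses.

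**Working it through.** The plan gives no figure on this point, so the check is a logic test, a trace of where the label is used, and one subtraction.

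**1. Logic test.** Let D mean that a drug cause is reasonably possible and O that another cause is. The Related sentence is grammatically broken, so both readings are tried. The literal reading is Related = D. The comparative reading is Related = D with the drug more likely than other causes. In both, Not Related = O.

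| D | O | Literal reading | Comparative reading |
|---|---|---|---|
| yes | no | Related | Related |
| no | yes | Not Related | Not Related |
| yes, drug leading | yes | both labels | both labels |
| yes, drug not leading | yes | both labels | Not Related only |
| no | no | neither | neither |

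On either reading O alone satisfies Not Related. An event with D and O both true can be given that label, and on the comparative reading it must be unless the drug leads. With Related = D and Not Related = no D, each row would receive exactly one label.

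**2. What depends on the label.**

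| Item | Depends on label? | Source |
|---|---|---|
| AE recording up to Follow-up | No | Protocol 6.5.2.1.6 |
| Follow-up of AEs leading to discontinuation | No | Protocol 6.3.1 |
| All-TEAE, severity, serious-TEAE and discontinuation tables | No | Protocol 8.7.2; SAP 8.7.1 |
| SAE form between Follow-up and day 30 | Yes | Protocol 6.5.2.1.6 |
| Follow-up of other ongoing AEs after participation ends | Yes | Protocol 6.5.2.1.6 |
| Related-TEAE tables, final and interim | Yes | Protocol 8.7.2; SAP 8.7.1, 8.9.2.5 |

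**3. Length of the label-dependent SAE window.** Window = 30 − (days from last dose to Follow-up). With Follow-up at 7 to 10 days (Protocol 6.1), this is 30 − 10 = 20 to 30 − 7 = 23 days. Protocol 6.3.1 and Table 2 instead count the 7 to 10 days from the end-of-treatment or early termination visit. If, as an assumption, dosing stopped 2 days before that visit (the SAP schedule allows visits ±2 days), Follow-up could fall on day 12 and the lower end becomes 30 − 12 = 18 days.

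**4. Do the SAE and table effects concern the same events?** Mostly not. In SAP 8.7.1 the TEAE window closes at the end-of-treatment or early termination visit or 7 days after the last dose, whichever is later. An SAE starting after Follow-up would generally be a non-TEAE and would stay out of a related-TEAE table under any definition.

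**The case against.** The strongest reply is that this is a drafting slip with narrow reach. The definitions are prefaced as general guidance after a long list of factors to weigh, and the word linking the two sentences suggests that they were meant as opposites. AEs up to Follow-up are recorded whatever the label. Missing causality counts as related (Protocol 8.7.2; SAP 8.7.1). Most safety tables ignore causality, and sodium is also summarised from laboratory values (SAP 8.7.2, 8.9.2.5). No dose-dropping rule in the documents refers to the related-event table. Protocol 6.5.2.1.7 also requires an SAE form whatever the relationship, and the Safety Management Plan, which is not among these documents, may add detail.

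Most of this stands, and it bounds the point. It does not supply a tie-break. The SAE sentence in 6.5.2.1.7 states no time window and sits beside a specific 30-day rule in 6.5.2.1.6 that is conditional on Related. The two pull in different directions.

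Three stronger readings are tempting and are not supported:

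- *The rule defaults to Not Related.* That holds only on the comparative reading with the drug not leading. Read literally, the rule is ambiguous.
- *Investigator and Sponsor judge by different rules.* Section 6.5.2.1.5 binds both. The test in 6.5.2.1.7 governs one further decision, IND safety reports. What is true is that the Sponsor holds two tests for the same serious event.
- *Related events are understated by some large share.* If a share q of plausibly drug-caused events also has a plausible alternative, up to q could move to Not Related. But the documents give no value for q, so the result only returns whatever is assumed.

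**Conclusion.** The defect is in the text: the two definitions overlap, leave a gap, and let an alternative cause alone justify Not Related. Its consequences are limited to SAE documentation in the 20 to 23 days between Follow-up and day 30 (given Follow-up 7 to 10 days after the last dose), follow-up after participation ends for events that did not lead to discontinuation, and the related-TEAE tables at the interim and final analyses. The 20 to 23 days measure the period in which the label decides documentation. They do not measure how many events would be mislabelled, which the documents do not allow anyone to estimate.

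A reader might infer that true drug events disappear from the safety data. Up to the Follow-up Visit they do not: they remain in the database, and those that are treatment-emergent remain in the all-TEAE tables by arm. The efficacy analyses are untouched. The conclusion assumes that no tie-break exists in form instructions or in the Safety Management Plan, neither of which was available.

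**What to change.** Replace both sentences in Protocol 6.5.2.1.5 with one standard and its complement, in line with 6.5.2.1.7:

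- Related: there is a reasonable possibility that study drug caused or contributed to the event, even if other causes are plausible.
- Not Related: there is no such reasonable possibility.

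Repeat the wording in the eCRF and SAE form instructions. Reconcile the 30-day SAE rule in 6.5.2.1.6, which applies only to events deemed Related, with the instruction in 6.5.2.1.7 to complete the form whatever the relationship, and state the time window to which each applies. Since both Investigator and Sponsor assess causality, also state whose assessment feeds the related-event tables.

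The cost is a few sentences in the protocol and form guidance. The downside is that more events will be labelled Related in all arms, including placebo, so the related-event tables should be read against the placebo column. New definitions would not remove the 30-day condition itself. They would make the judgement on which it turns well defined.

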6.5.2.1.6 Adverse Event Documentation and Follow-up

All adverse events, including observed, elicited, or volunteered problems, complaints, or symptoms are to be recorded on the adverse event page in the patient’s eCRF from the time the patient signs the ICF until the Follow-up Visit/early termination, whether or not judged by the Investigator to be related to study drug. The need to capture this information is not dependent upon whether adverse events are related to study drug. Serious adverse events that occurred up to 30 days after the last dose of study drug need to be documented on an SAE Report Form if they are deemed by the Investigator to be “Related” to study drug.

Each adverse event is to be documented with a verbatim/reported term, start and stop date, severity, causal relationship to study drug, action taken with study drug, and outcome (resolved, resolved with sequelae, resolving, not resolved, fatal, unknown). The Investigator must review new adverse events and the outcome of ongoing adverse events frequently throughout the study.

In addition to recording all adverse events (serious and non-serious) in the patient’s eCRF, all SAEs must also be documented on the SAE Report Form for the study.

The Investigator will follow all adverse events until they resolve, the Investigator assesses them to be stable, or the patient’s participation in the study ends, whichever comes first. In addition, the Investigator will follow all adverse events assessed as related to study drug that are ongoing at the time of the patient’s last visit, until they resolve or the Investigator assesses them as stable, even if the patient’s participation in the study has ended. Resolution of such events is to be documented in the patient’s record as appropriate.

It is anticipated that some patients may undergo procedures and/or experience events that are common in the study population under investigation, independent of study therapy. Preplanned procedures and procedures (eg, kidney transplant or catheter replacement) or events that are independent of study therapy, according to the Investigator’s assessment, will be documented as specified in the Safety Management Plan.

